## **10.4. Risk factor analysis using prospective methods**

## **10.4.1. Exposure variables**

- HLA
- Diet
- Psychological Distress
- Clinical events

## **10.5.** Risk factor analysis using case-control methods

## **10.5.1. Exposure variables**

- Viral exposure
- Bacterial exposure
- Dietary Biomarkers
- Inflammatory Markers

## 10.5.2. Matching Criteria

As part of the study design of the case-control studies controls will be matched to cases on several confounding factors. This will be done to achieve a more statistically efficient analysis. The factors that are being considered as possibilities to match on are:

- HLA type
- Study center
- Duration of follow-up
- Completeness of data including serial biological samples
- Season of birth

## **10.5.3. Statistical Considerations**

For the study of risk factors for the development of autoimmunity, those subjects developing autoimmunity will be cases and those not developing autoimmunity at that time will be controls (population density sampling). For each case, we will attempt to identify k controls (see below for considerations for the determination of k) that are matched to the case on study center, gender, and HLA type. Cost efficiency is achieved by determining the values of the laboratory parameters only for the cases and the chosen matched controls. We will then perform stratified

logistic regression using the matched sets as strata in order to study the effect of various possible risk factors, univariately and multivariately, on the odds of developing autoimmunity. Note that this analytic method does not require that every matched set contain exactly k controls. We can have varying numbers of controls for each case. Thus while we will attempt to have the same number of controls for each case, we will allow for fewer controls for cases with fewer matches and will choose more controls, to compensate, for those cases with more matches.

For the study of risk factors for the development of T1DM, we will consider those who developed T1DM by age 15 to be cases. For those who also developed autoimmunity as well, we will use the same controls as were chosen for the study of autoimmunity. The same analytic methods will be used.

The number of controls needed per case will depend, of course, on the number of cases and thus cannot be fully determined until the end of the planned follow-up periods. One plausible scenario, given in Table 14, assumes that for the pooled sample we would have 5.5% conversion by age 15 to diabetes among those exposed to a risk factor, that 20% would be exposed, that the hazard ratio for the risk factor is 2.0, and that 0% would be lost to follow-up. This would lead to about 460 cases.

The following tables presents the power for a case control study with 1-3 controls per case, odds ratio = 1.5 and 2.0, and 380 - 500 cases.

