#### 7. Screening procedures

#### 7.1. HLA typing

#### 7.1.1. HLA screening

Genotype screening will be performed using either a dried blood spot (DBS) punch or a small volume whole blood lysate (WBL) specimen format. Screening blood sample will be obtained generally at birth as a cord blood sample, but potential participants, especially first-degree relatives of T1DM patients can be screened using heel stick capillary sample up to the age of 4 months. This exception is made to maximize the number of newborn relatives participating in this study. The experience of the ongoing studies, such as DAISY and BABY-DIAB is that some families with a diabetic proband learn about those studies after

the baby is born, but are extremely interested in participation. These studies have also found that relatives are at a higher risk of T1DM than high-risk newborns from the general population, even stratifying for HLA-DR,DQ genotypes, and that these families are much less likely to drop out from prospective follow-up, thus particularly valuable to TEDDY. After PCR amplification of exon 2 of the HLA Class II gene (DRB1, DQA1 or DQB1), alleles will be identified either by direct sequencing, oligonucleotide probe hybridization, or other genotyping techniques. Additional typing to sufficiently identify certain DR-DQ haplotypes is as specified in Section 6.1 above.

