T1DM (referred to as cases) we will randomly select k subjects who did not convert to autoimmunity or T1DM (controls). The sampling for the selection of matched controls is based upon incidence density sampling which allows the comparison of cases with a subset of the cohort at risk of being cases at the time when each case occurs, or equivalently matches cases and controls for the duration of follow-up. Since controls selected in this way may become cases over time, we will employ over sampling of controls and may select different controls at different points in time.

We will then compare these cases to controls as a matched case control study using conditional logistic regression. The value of k will be determined in order to have at least 80% power based on tables 14 -16, taking into consideration the number of cases available for the analysis. Thus, these expensive determinations will be made only on the cases and their chosen matched controls. Matching will be based on HLA type, study center, duration of follow-up, and completeness of data including serial biological samples. Every effort will be made to use the same controls for multiple case-control studies. This will allow inclusion of all key exposures simultaneously in the analytical model and exploration of confounding, effect modification, and interactions between exposures. The standard set of controls will include only those with complete data/samples for all components of the protocol. Since we do not need to have the same number of controls for each case, we will strive for an average of k controls for each case – not exactly k for each case. These analyses will also be performed in both a univariate and multivariate fashion. Odds ratios for each factor will be computed, as will their 95% confidence intervals. ROC curves for sensitivity vs. 1 specificity based on combinations of these factors will be computed. Here sensitivity refers to the ability of the factors to predict conversion to the study endpoint among those who do convert and specificity refers to ability to predict conversion free survival among those who are.

Similar analyses will be performed for development of autoimmunity and T1DM. Since the cases for T1DM will be a subset of the cases for autoimmunity, we will attempt to use the same controls. However, since there will be fewer cases, additional controls will be needed. Again, the (average) number of controls per case will be guided by tables 14 - 16.

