The following is a non-exhaustive listing of planned statistical analyses for the prospective part of the project:

- 1. We will classify infants as to whether or not they had early exposure to cereals or gluten in the diet (vs. those receiving only breast milk for the first 3 months). Those exposed will be compared to those not exposed using the Log Rank Test.
- Subjects will be classified, based on diet questionnaires, as consuming low or high levels of anti-oxidants such as carotenoids, ascorbic acid, and selenium. Those with low levels will be compared to those with high levels with respect to the development of T1DM and autoimmunity using Log Rank Tests.

- 3. Subjects' drinking water will be analyzed and subjects classified as drinking water with high or low concentrations of zinc, and nitrate and as low or high pH. Groups will be compared using the Log Rank Test.
- 4. Cox Regression will be used to study the association of the level of psychosocial stress with the development of T1DM and autoimmunity.

The following analyses will be performed in the nested case control portion of the study:

- The association between the number of enterovirus infections a child has and the development of T1DM and islet autoimmunity will be studied with Cox Regression. Using zero as the reference, dummy variables will be created to represent 1, 2, etc infections. The hazard ratios of these values relative to zero will be estimated and p values of the estimates computed. The same type of analyses will be done for the number of rotavirus infections.
- 2. Low levels of omega-3 fatty acids, EPA, and DHA in children's erythrocyte membranes have been associated with increased risk of islet autoimmunity. The odds ratio for each of these exposures will be estimated.
- 3. Low levels of alpha-tocopherol has been associated with increased risk of islet autoimmunity. The odds ratio for each of this exposure will be estimated

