Ov	er 5 years	General Population	on FDF	ł			
Enroll		7,013	788				
Cases - autoantibodies by age 6		281 (4%)	105 (13.	3%)			
Cases - T1DM by age 15		281 (4%)	105 (13.	3%)			

Based on submissions by the participating institutions, we expect to be able to enroll 7,013 subjects from the general population and 788 relatives in five years. Those from the general population and the relatives are expected to have about 4% and 13.3% autoimmune conversion at 6 years respectively. Tables 6-13 below give the power for a Log Rank Test at a two-sided 0.01 significance level for the general population subjects, the relatives, and the pooled sample accrued over 5 years with 15 years of post-accrual follow-up for dichotomous pre-birth triggers of frequencies 1%, 5%, 10%, and 20% and hazard ratios of 1.5 and 2.0 and losses to follow-up at rates of 0%, 2%, 5%, and 10% per year. These calculations are based on the method of Lakatos (Lakatos, 1998) using a computer program described by Cantor (Cantor, 2003).

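### First-degree-relative status is in none of the three differing matching lists and is not a log-rank stratum, so univariate results are open to confounding by family history

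*Protocol*

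**What the plan says.** The protocol describes matching in three places:

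- Section 10.1: "Matching will be based on HLA type, study center, duration of follow-up, and completeness of data including serial biological samples".
- Section 10.5.2: the same four factors plus "Season of birth", introduced as candidates under consideration.
- Section 10.5.3: controls "matched to the case on study center, gender, and HLA type".

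FDR status appears in none of them.

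On risk, Section 7.1.1 reports from earlier cohorts that "relatives are at a higher risk of T1DM than high-risk newborns from the general population, even stratifying for HLA-DR,DQ genotypes". Section 10.3 plans for a large difference: "Those from the general population and the relatives are expected to have about 4% and 13.3% autoimmune conversion at 6 years respectively". The case table there uses the same two percentages for diabetes by age 15.

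For the prospective part, Section 10.1 says of early cereal or gluten exposure: "Those exposed will be compared to those not exposed using the Log Rank Test". Antioxidant intake and drinking water are handled the same way. A continuous factor that appears to violate proportional hazards is dichotomised and moved from Cox regression to the log-rank test. No stratification is mentioned. Section 10.3 gives power for a "Log Rank Test at a two-sided 0.01 significance level for the general population subjects, the relatives, and the pooled sample".

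**The concern.** A variable that predicts the outcome and also differs between exposed and unexposed children distorts a crude comparison. By the protocol's own figures, FDR status meets the first condition: relatives are 10% of the planned cohort and 27% of the expected cases. By Section 7.1.1, matching on HLA does not fully remove this. The second condition is plausible for feeding, supplements or household water, because families with an affected member may behave differently, but the protocol gives no exposure frequencies by family history.

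The plan looks for hazard ratios of about 2 and also tabulates 1.5. A spurious ratio of 1.2 to 1.3, tested at 0.01, is not negligible on that scale. In the case-control part, expensive assays are run only on cases and their chosen controls, so a poor matching rule is costly to repair later. The lists also differ on gender, season of birth and completeness of data, so centres or analysts working from different sections would draw different controls.

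**Working it through.** **Inputs.** Section 10.3: "we expect to be able to enroll 7,013 subjects from the general population and 788 relatives in five years", at 4% and 13.3%. Section 7.1.3: families of HLA-eligible infants are told about 1 in 20 (general population) and 1 in 12 (relatives). Exposure prevalences are assumed, since the protocol gives none by FDR status.

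**The plan's own figures.** 7,013 × 0.04 = 280.5 and 788 × 0.133 = 104.8, matching the stated 281 and 105. Relatives are 788/7,801 = 10.1% of children and 105/386 = 27.2% of cases.

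**Risk ratio.** Crude: 13.3/4 = 3.325. From the risks told to families: (1/12)/(1/20) = 1.67. Section 7.1.1 gives a direction within HLA genotype but no size.

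**Crude pooled risk ratio for a null exposure.** With prevalence p in the general population, q in relatives, and R the relatives' risk ratio:

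- exposed risk = 0.04 × (7,013p + R·788q) / (7,013p + 788q)
- unexposed risk: the same with 1−p and 1−q

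At R = 3.325, p = 10%, q = 20%: exposed 0.04 × (701.3 + 3.325 × 157.6)/858.9 = 5.71%; unexposed 0.04 × (6,311.7 + 3.325 × 630.4)/6,942.1 = 4.84%; ratio 1.18. At q = 30%: 6.34% against 4.75%, ratio 1.34.

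**Type I error.** The shift of the test statistic is (D₁ − Dx)/√(Dx(1−x)), where D is total events, D₁ exposed events and x the exposed fraction. For q = 20%: (49.01 − 385.3 × 0.1101)/√(385.3 × 0.1101 × 0.8899) = 1.07. Against the two-sided 0.01 critical value of 2.576 this gives 6.6%. For q = 30% the shift is 2.06 and the error 30.4%. Simulation of the unstratified test gives slightly more, hence the ranges.

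| Prevalence, relatives vs others | R = 3.3: ratio; type I error | R = 1.67: ratio; type I error |
|---|---|---|
| 10% vs 10% | 1.00; 1% | 1.00; 1% |
| 20% vs 10% | 1.18; 7–9% | 1.06; about 2% |
| 30% vs 10% | 1.34; 30–33% | 1.11; about 4% |

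At 15% vs 10% the simulated error is about 3% at R = 3.3 and just above 1% at R = 1.67.

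**Does centre matching remove it?** From the enrolment figures in Table 5, the share of relatives is 236/563 = 42% in Germany but 5% (Sweden, 118/2,240) to just under 11% (Washington, 137/1,306) elsewhere. Take R = 3.3 at every centre, three controls per case and matching on centre only, with HLA not modelled. Cases are then 27% relatives and controls about 12%. The null odds ratio is about 1.16 (error about 4%) at 20% vs 10%, and 1.30 (about 16%) at 30% vs 10%. At R = 1.67 it is 1.05 to 1.10, with error 1.3% to 2.0%. Centre matching removes part of the imbalance, not all.

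**Cost of stratifying.** A Lakatos-type calculation with exponential hazards, five years' accrual and 15 years of follow-up after accrual reproduces the plan at 10% exposed, hazard ratio 1.5 and no loss: 0.522 (Table 6 states 0.52) and 0.748 (Table 8 states 0.75). In the same cell, with the group-specific rates, power is 0.689 stratified by FDR status. Unstratified at the blended rate of 4.94%, it is 0.692.

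**The case against.** Much can be said for the plan. Cox and conditional logistic models are to be run multivariately as well as univariately, and shared controls are meant to allow confounding to be explored. Family history is itself listed as a log-rank factor, so it is collected. Differences between children with and without affected relatives are a secondary objective (Section 4) and part of the second hypothesis (Section 5). Section 10.3 powers the two groups separately as well as pooled, and Section 10.1 does not say that each log-rank test pools them. Covariate sets are commonly left to the statistical analysis plan, which is not at hand. Genotypes e–j in Section 6.1.3 admit relatives only, so genotype-level HLA matching already fixes FDR status there.

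All of this stands, and it rules out two stronger readings:

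- A reader might infer a threefold risk within HLA type. The 3.3 is a crude contrast, and relatives may enter on genotypes closed to others. No within-HLA size is given, and the risks told to families imply about 1.67.
- A reader might infer that the study's results are confounded. That requires an exposure that differs by FDR status and is left unadjusted, and the documents establish neither.

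The conflict between the lists can also be overstated. Section 10.5.2 offers candidates only, and the density sampling in Section 10.5.3 already aligns duration of follow-up.

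What remains is narrower. Testing family history as a factor does not adjust other exposures for it. Univariate results are reported alongside the multivariate ones. A factor moved to the log-rank test for non-proportionality has no adjustment described. Genotypes a–d admit both groups.

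**Conclusion.** The point holds as an omission with an inconsistency: FDR status is in no matching list and is not a log-rank stratum, and the lists differ on gender, season of birth and completeness. Univariate and log-rank results are open to confounding for exposures that differ by FDR status.

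The size depends on two things that the protocol does not fix: the exposure difference between relatives and others, and the risk ratio that applies. The distortion runs from none (equal prevalence), through small (1.06 to 1.11 at a ratio of 1.67), to material (1.18 to 1.34 at the crude ratio), in the crude pooled test. In the matched part, centre and HLA matching reduce it. Restricting controls to those with complete data may also change the share of relatives among controls, since Section 7.1.1 expects these families to drop out less; the documents do not allow this to be sized.

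**What to change.** 1. State one matching list and use it identically in Sections 10.1, 10.5.2 and 10.5.3. Include FDR status (yes/no), and decide explicitly on gender, season of birth and completeness.
2. Where relatives have too few eligible controls, use the variable number of controls that Section 10.5.3 already allows, or make FDR status a mandatory covariate in the conditional logistic model.
3. Stratify every log-rank test that pools relatives and general population at least by FDR status, including tests that replace Cox regression after a proportional-hazards check.
4. Handle centre or country and HLA group by stratification or, where cells are sparse, by adjustment in a Cox model. Full cross-stratification by centre, HLA group and FDR status would spread about 105 expected cases among relatives over many cells, and its power cost has not been calculated.

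The cost is a wording change, fewer eligible controls for relatives at small centres (57 relatives planned in Georgia/Florida), and about 0.3 percentage points of power from FDR stratification in the cell checked.

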# Table 14: Power Table for 1 Control per Case

	Power with 1	Control p Alpha	
	Exposure	Power	Power
	among	(OR =	(OR =
	Controls	1.5)	2.0)
380 Cases	.05	.11	.43
000 04363	.10	.22	.75
	.15	.33	.89
	.20	.00	.95
	.20	.41	.95
400 Cases	.05	.11	.45
400 00000	.10	.23	.78
	.15	.34	.91
	.20	.43	.96
	.20	.40	
420 Cases	.05	.11	.47
	.10	.24	.80
	.15	.36	.93
	.20	.46	.97
440 Cases	.05	.12	.50
	.10	.26	.83
	.15	.38	.94
	.20	.48	.97
460 Cases	.05	.13	.52
	.10	.27	.85
	.15	.40	.95
	.20	.50	.98
480 Cases	.05	.13	.55
	.10	.29	.87
	.15	.42	.96
	.20	.53	.98
500 Cases	.05	.14	.57
	.10	.30	.88
	.15	.44	.97
	.20	.55	.99

# Table 15: Power Table for 2 Controls per Case

	Power with 2 Alp	Controls ha = .01	per Case
	Exposure	Power	Power
	among	(OR =	(OR =
	Controls	1.5)	2.0)
		,	,
380 Cases	.05	.17	.62
	.10	.34	.89
	.15	.48	.97
	.20	.58	.99
400 Cases	.05	.18	.65
	.10	.36	.91
	.15	.50	.98
	.20	.60	.99
420 Cases	.05	.19	.68
	.10	.38	.93
	.15	.52	.98
	.20	.63	.99
440 Cases	.05	.20	.70
	.10	.40	.94
	.15	.55	.99
	.20	.65	1.0
100.0	0.5		70
460 Cases	.05	.21	.73
	.10	.42	.95
	.15	.57	.99
	.20	.68	1.0
480 Cases	.05	.22	.75
400 04363	.10	.44	.96
	.15	.59	.99
	.20	.70	1.0
	.20	.70	1.0
500 Cases	.05	.23	.77
	.10	.45	.97
	.15	.62	.99
	.20	.72	1.0
	.20	• • •	

82

## Table 16: Power Table for 3 Control per Case

Power	with	3	Controls	per	Case
			Alpha = .	.01	

	Exposure	Power	Power
	among	(OR =	(OR =
	Controls	1.5)	2.0)
380 Cases	.05	.21	.70
	.10	.40	.93
	.15	.55	.98
	.20	.65	1.0
400 Cases	.05	.22	.73
	.10	.42	.95
	.15	.57	.99
	.20	.67	1.0
420 Cases	.05	.23	.76
	.10	.44	.96
	.15	.60	.99
	.20	.70	1.0
440 Cases	.05	.25	.78
	.10	.46	.97
	.15	.62	.99
	.20	.72	1.0
460 Cases	.05	.26	.80
	.10	.48	.97
	.15	.64	1.0
	.20	.75	1.0
480 Cases	.05	.27	.82
	.10	.51	.98
	.15	.67	1.0
	.20	.77	1.0
500 Cases	.05	.28	.83
	.10	.53	.98
	.15	.69	1.0
	.20	.79	1.0

## **10.6. Gene-environment interactions**

While the description of the analytic plan addresses univariate analyses of possible triggers of autoimmunity and T1DM, clearly the interactions of environmental exposures and genetic variability are of keen interest. Multivariate models, including time-dependent covariates, are planned. A variety of models are posited to include Cox Proportional Hazards, generalized estimating equations for longitudinal analyses and general linear models.

#### **10.7.** Criteria for the termination of study

Criteria for termination of the study would fall into the following categories: lack of feasibility, achievement of planned accrual and follow-up, analytic results that demonstrate a clear and unequivocal environmental and/or genetic basis for autoimmunity or T1DM, or successful attainment of planned study end points. Subject accrual and protocol compliance with respect to collecting the planned samples and study information will be monitored on a continuing basis. It would be anticipated that start-up will be gradual and that estimates of the projected accrual rates may not become stable for the first year after the study begins. Should these estimates differ from planned, then discussion will be held with the Principal Investigators from the clinical centers to address ways in which to improve or augment accrual rates. Similarly, if the estimates of protocol non-compliance exceed those identified in the tables, an action plan will be developed to make necessary improvements and corrections. If the combination of these efforts still result in projections that the study will not have adequate statistical power to detect a risk factor with odds ratios of 5 or less, then the feasibility of the study becomes questionable and both the study group and the External Advisory Board will be presented with the information for possible action.

#### 10.8. Procedure for accounting for missing, unused, and spurious data

Every effort will be made to obtain complete ascertainment of study data as defined by the protocol. All data will be subject to careful error checking (ranges and consistency) to identify possible spurious data for correction. Efforts to account for missing data will be based upon accepted techniques so as to not introduce bias into the study. An important component is the ability to ascertain study end points from subjects who may not wish to continue participation with planned study follow-up. The study benefits in this regard from diabetes surveillance programs available in four of the clinical sites: the SEARCH for Diabetes in Young (covering all Colorado and part of the state of Washington population) as will national diabetes registries in Finland and Sweden. These registries are ongoing sources to obtain data on children developing diabetes who were either not followed or may have dropped out from the study.

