#### **ORGANIZATION:**

A network of collaborating investigators following common protocol(s) was created to allow for a coordinated, multi-disciplinary approach to this complex problem.

- Clinical Centers (6 participating centers): Colorado Barbara Davis Center, Univ. CO, Denver, CO Finland University of Turku, Turku, Finland Georgia/Florida Augusta University, Augusta, GA Germany Diabetes Research Institute, Munich, Germany Sweden Lund University, Malmö, Sweden Washington Pacific Northwest Diabetes Research Institute, Seattle, WA
- Data Coordinating Center University of South Florida, Tampa, FL

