at-risk infants, Edinburgh Postnatal Depression Scale scores were reliable ( $\alpha = .89$ ) and predictive of the mother's understanding of risk (higher depression scores were associated with underestimating risk), anxiety (higher scores were associated with higher anxiety) and study drop out (higher scores were associated with early study drop-out) (Hood, 2003). A brief 6-item Depression Scale from Bradley's Well-Being Questionnaire will be included in the self-administered parent questionnaire completed at the 15 - and 27-month study visits. This scale has been previously used in World Health Organization (WHO) studies and has been translated into several languages.

After 27 months, we propose to collect measures of parental psychological stress/function annually. We will conduct an interim analysis of data collected from the primary caretaker through 27 months to guide us in terms of retaining the psychological stress/function measures or adding new ones.

At 39 months, we will add questions to the parental/primary caretaker's annual assessment that address the parent's or primary caretaker's perceptions of the child's function and well-being (e.g., does the caretaker overprotect, stigmatize or treat the child differently because the child is atrisk for diabetes). Under consideration are Parsons et al's (2002) rejection/protection index and adjective checklist approach used with four year old boys with Duchenne muscular dystrophy identified through newborn screening. However, since it will be more than three years before these assessments will be conducted, in two years we will conduct a through review of the available literature to identify the best available instrument for this purpose.

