## 10.1. Master Plan of Analysis

The primary goal of the statistical analyses to be performed as part of this study will be the identification of factors associated with the development of autoimmunity and T1DM. In order to accomplish this, we will employ two different types of analysis, depending on the nature of the factor being studied.

- For those factors whose values will be known to us without additional costs, we will perform log rank tests and Cox Proportional Hazards Regressions. For these analyses, the dependent variable will be the age at which the event being studied (development of autoimmunity or diagnosis of T1DM) occurred. Those not achieving the event when the analyses are being performed and those lost to follow-up without achieving the event will be considered censored as of the date last known to be event-free. The log rank test will be used to study factors with a few discrete values. For example:
  - (a) Family History
  - (b) Haplotype
  - (c) Breast-feeding

For factors with continuous values, we will test for conformity of those values with the proportional hazards assumption by examining the significance of the interaction of the time variable (treated as a time-dependent covariate) with the factor. If there is an indication of a non-zero interaction coefficient, (p < 0.10) we will dichotomize the variable and use the log rank test instead of proportional hazards regression. Otherwise, we will use proportional hazards regression to test for significance at the .01 significance level. The following are examples of factors to be studied in this manner:

- (a) Amounts of certain nutrients consumed
- (b) Duration of breast feeding
- (c) Maternal anxiety and depression as measured by the State Trait Anxiety Inventory and the Edinburgh Postnatal Depression Scale

Proportional hazards regression will be used in both a univariate and multivariate manner and reported both ways. For each factor studied, estimated hazard ratios and their 95% confidence intervals will be computed. When a set of factors that predict conversion to T1DM or autoimmunity are determined as described above, we will compute estimated "survival" curves for subjects having specific factor profiles.

2) For those factors whose determination is costly we will employ a nested casecontrol design. At the time at which a cohort subject converts to autoimmunity or

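### Registries add late diabetes cases among children who leave the study, but no rule adds the matching event-free time for leavers who stay healthy, so T1DM hazard ratios are biased wherever dropout differs by exposure

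*Protocol*

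**What the plan says.** **Protocol 10.8** treats end points in withdrawn children as something to be recovered: "An important component is the ability to ascertain study end points from subjects who may not wish to continue participation with planned study follow-up". It then names the means: "The study benefits in this regard from diabetes surveillance programs available in four of the clinical sites". These are a US surveillance project, "covering all Colorado and part of the state of Washington population", and national registries in Finland and Sweden. Georgia/Florida and Germany have none. The registries' contribution is described as "These registries are ongoing sources to obtain data on children developing diabetes who were either not followed or may have dropped out from the study", that is, as cases. Nothing is said about children who leave and are not listed.

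**Protocol 10.1** sets the time variable for the prospective log-rank and Cox analyses as age at the event. For the rest, "those lost to follow-up without achieving the event will be considered censored as of the date last known to be event-free".

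**On dropout**, 8.12.4.7 lists family history, study site, parental depression and negative life events among the likely predictors of leaving, and high parental anxiety as a likely predictor of staying. In 8.12.4.3.1 an earlier cohort of mothers with at-risk infants is cited for depression: "higher scores were associated with early study drop-out". Section 7.1.1 says of families with an affected relative that "these families are much less likely to drop out from prospective follow-up". Section 10.1 names family history as a log-rank factor, maternal anxiety and depression as Cox factors, and psychosocial stress as a planned Cox analysis of T1DM.

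**The concern.** Take two children who leave at age 3 at a registry site. One is registered with T1DM at 9 and contributes nine years and an event. The other stays healthy and, unless registry absence counts as evidence, contributes three years. Follow-up is lengthened only for children already known to be cases. At a site without a registry both stop at 3.

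This has two consequences. Within registry sites, the group that leaves more often loses event-free time but keeps its events, so its apparent hazard rises. Between sites, those with a registry show a higher T1DM rate at equal true risk.

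T1DM is the second primary outcome. Several factors to be tested against it are ones the protocol itself expects to be linked to dropout, so a false trigger or a falsely protective factor could be reported.

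**Working it through.** **Inputs from the protocol.** T1DM risk is 4% by age 15 (Table 6), so the yearly hazard is λ = −ln(0.96)/15 = 0.00272. Yearly loss is 0, 2, 5 or 10% (10.3). Planned enrolment in Table 5, general population plus relatives:

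- Colorado 1,312 + 113 = 1,425
- Finland 1,384 + 127 = 1,511
- Sweden 2,122 + 118 = 2,240
- Washington 1,169 + 137 = 1,306

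The sum is 6,482 of 7,801 (83%). Without Washington it is 5,176 (66%).

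**Assumptions, not in the protocol.** 20% exposed, true HR 1.0, loss that differs by exposure, and the share of dropouts' diabetes that is recovered.

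**The plan's own figures.** The protocol gives no figure for this bias. As a check on reading its rates, Table 6 (HR 2.0, 5% exposed, loss 0/2/5/10%) states power 0.89/0.82/0.71/0.52. A Lakatos-type log-rank calculation with exponential events and loss gives 0.890/0.821/0.704/0.520, using 5 years of accrual plus 15 years after it.

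**Apparent hazard under the plain reading.** Let d be the yearly loss rate, G = exp(−dt) the share still attending at age t, and k the share of dropouts whose T1DM would be recovered. Among children free of T1DM at age t:

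- events occur at rate λ[G + k(1−G)];
- the share at risk is G + k(1−G)(1 − exp(−λ(15−t))), because a dropout stays at risk only if he or she later becomes a recovered case.

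The apparent hazard is the first divided by the second. With k = 1 and a rare event it is close to λ/G = λ·exp(dt). The false HR at age t is then about exp((d₁−d₀)t), where d₁ is loss in the exposed and d₀ in the unexposed. At the mid-age of 7.5 years, 5% vs 2% gives exp(0.03 × 7.5) = 1.25, and 10% vs 5% gives exp(0.05 × 7.5) = 1.45.

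**Cox estimate.** Solving the large-sample Cox score equation over ages 0 to 15 with these two quantities gives the HR for a factor with no effect:

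| Loss per year, unexposed vs exposed | k = 1 | k = 0.83 | k = 0.66 | k = 0.5 |
|---|---|---|---|---|
| 0% vs 2% | 1.16 | 1.13 | 1.10 | 1.08 |
| 2% vs 5% | 1.24 | 1.20 | 1.17 | 1.13 |
| 5% vs 10% | 1.42 | 1.36 | 1.31 | 1.24 |
| 5% vs 2% | 0.80 | 0.82 | 0.85 | 0.88 |

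The columns 0.83 and 0.66 are full capture with Washington counted in or out. Equal loss in both groups, or k = 0, gives 1.00. A simulation of 2 million children at 2% vs 5% gave 1.23 with full coverage and 1.20 with 83% coverage. At N = 7,013 and full capture, the two-sided 0.01 test rejects a true null in about 13% (2% vs 5%) and 41% (5% vs 10%) of studies. Incomplete coverage lowers these rates.

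**Registry against non-registry site.** With equal true risk and equal loss, mean attended time is (1−exp(−15d))/d, so the crude rate is inflated by 15d/(1−exp(−15d)): 1.16, 1.42 and 1.93 at 2, 5 and 10%. The Cox values are 1.15, 1.41 and 1.89.

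**Under one rule.** If every dropout is censored at leaving, events occur at λG and the share at risk is G. If every dropout is carried to linkage, the values are λ and 1. Both return λ whatever d is, so the HR is 1.00 (0.99 in the simulation under either rule).

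**The case against.** The strongest reply is that 10.1 never says last contact. It says the last date known to be event-free, and where a registry covers the whole population, absence from it could make the linkage date that date. Cases and non-cases would then be treated alike and the bias would vanish. Section 10.8 also names a data source and does not expressly put registry cases into the Cox model. It includes children who were never followed, who could not enter that model anyway, and it promises recognised methods that avoid bias. Details of this kind can be left to an SAP.

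Part of this stands: censoring at last contact is an inference. But the protocol states both halves, recovery of end points in withdrawn children and censoring of the rest, and describes the registries only as sources of cases. Nothing links non-listing to an event-free date. The two readings give different hazard ratios, and partial coverage in Washington means absence there would not always be informative.

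A reader might infer more than the text supports:

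- **That anything predicting dropout will appear to cause T1DM.** Loss must differ by exposure, the effect arises only where a registry exists, and a factor linked to staying looks protective.
- **That secondary objectives 1 and 2 are biased outright.** They compare environmental determinants between populations, not baseline hazards. A site-level shift does not by itself bias an exposure effect estimated within a site.
- **That the whole study is affected.** Diabetes registries do not touch the autoantibody end point. The nested case-control part, which holds all biomarker tests, matches on center and duration of follow-up, which limits the problem there.

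The dropout evidence also comes from earlier studies. Section 8.12.4.7 calls its list likely candidates, and 10.2.2 plans continuous comparison of dropouts with those who stay.

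**Conclusion.** The concern holds for the prospective log-rank and Cox analyses of T1DM. Followed as written, 10.1 and 10.8 let a child's length of follow-up depend on the outcome at the centers with registries. The HR is biased upward for a factor that raises dropout and downward for one that lowers it. Parental depression and negative life events would be pushed up. Family history would be pushed down, since relatives are expected to leave less. Stratifying by center removes the contrast between registry and non-registry sites but not the bias within registry sites.

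The size is moderate and depends on assumptions. A difference of 2 against 5% per year gives a false HR of about 1.2, and 5 against 10% about 1.4. Small differences or poor capture give values near 1.1. The overall loss rates are the protocol's. Their split by exposure, the 20% exposed and the capture rate are not in the document, so the hazard ratios and rejection rates are illustrations and not forecasts.

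**What to change.** State in 10.1 and 10.8 one rule that does not depend on the outcome:

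- **(a)** censor every dropout at the last TEDDY contact, whether or not a registry later lists the child; or
- **(b)** in registry-covered areas, carry every linkable dropout, listed or not, to the linkage date, and censor all dropouts elsewhere (Georgia/Florida, Germany, uncovered parts of Washington) at last contact.

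Stratify by clinical center under either rule. Name one as primary and report the other as a sensitivity analysis. Registry cases should never enter without the event-free time of the other dropouts.

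The change itself is one of wording. Rule (a) gives up registry events in the primary analysis. The share recovered only after dropout is 1 − [λ/(λ+d)](1 − exp(−15(λ+d)))/0.04, which is 13.5%, 29.5% and 48.0% at 2, 5 and 10% loss. With 20% exposed, that is 0.8 × 13.5 + 0.2 × 29.5 = 17% of events at registry sites for 2% vs 5%, and 0.8 × 29.5 + 0.2 × 48.0 = 33% for 5% vs 10%. Rule (b) keeps those events but relies on registry completeness and on consent to linkage from families who have left.
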